1.2. Study Design

1.2.1. Overall Study Design

This is an international Phase 3, open-label 28-week extension study to evaluate the safety and efficacy of vibegron 75 mg in men with symptoms of OAB on stable doses of pharmacological therapy for BPH. This study is an extension for subjects who have completed the Phase 3, double-blind, randomized, 24-week Study URO-901-3005.

Approximately 300 men with symptoms of OAB on stable doses of pharmacological therapy for BPH who completed 24 weeks in Study URO-901-3005 and continue to qualify for this study may be permitted to enroll in this extension study, from approximately 60 study sites.

During this extension study, subjects who had been randomized in Study URO-901-3005 to receive vibegron 75 mg will continue their same treatment once daily for an additional 28 weeks, and subjects who had been randomized in Study URO-901-3005 to the placebo group will receive study treatment of vibegron 75 mg once daily for 28 weeks during the extension. Thus, through participation in both the URO-901-3005 and URO-901-3006 (extension) studies, subjects originally randomized to vibegron will receive 52 weeks total of vibegron treatment, and subjects originally randomized to placebo will receive 28 weeks total of vibegron treatment.

[figure not shown]
Study visits will be named to reflect continuation from Study URO-901-3005, with the first study visit of this extension study occurring at Week 24. Following enrollment in this extension study, subjects will return to the clinic for visits at Week 28, Week 36, and Week 52 (all relative to Day 1 of Study URO-901-3005). A telephone contact will occur at Week 44 to review AEs/serious AEs (SAEs) and concomitant medications.

This study consists of a 28-week open-label Treatment Period. Unscheduled Visit(s) may be arranged as needed.

A Data Safety Monitoring Board (DSMB) will be retained to assess, on an ongoing basis, all safety aspects of this study. This will be an external independent DSMB that monitors the safety for both Study URO-901-3005 and Study URO-901-3006. The detailed activities including meeting plans will be described and documented in the DSMB Charter. A separate statistical analysis plan will be prepared for the DSMB.

The study schema is shown in [Figure 1](#).

Figure 1: Study Schema

*Week 44 consists of a telephone contact to review AEs/SAEs and concomitant medications; no clinic visit is required at that timepoint.

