3.1.2. Safety Analysis Set Extension

The Safety Analysis Set Extension (SAF-Ext) will serve as the primary population for the analysis of safety data in this trial.

The SAF-Ext consists of all randomized subjects in Study URO-901-3005 who

- a) have completed the 24-week treatment period in the Study URO-901-3005, and
- b) enrolled into the extension Study URO-901-3006 and received at least one dose of vibegron in this study.

Safety endpoints will be descriptively summarized for the entire Safety Analysis Set Extension. No imputation will be performed for missing safety data. Baseline will be established as the last observation prior to the first dose of vibegron. All safety data collected on or after the first exposure to vibegron within the combined experience of the patient on URO-901-3005 and

URO-901-3006 will be included in the safety analysis for URO-901-3006, and all analyses by visit will index visits from the first dose of vibegron on either study; subjects who received placebo in study URO-901-3005 will only contribute safety data up to Week 28.

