4.2.2. Reporting Conventions

General rules

In general, all collected safety data and any derived efficacy and PRO data will be presented in subject data listings for all enrolled subjects. This includes all data collected on the parent study, URO-901-3005, relevant to the definition of baseline and all data collected on URO-901-3005 after the first dose of vibegron, excluding assessments not repeated during 3006 (orthostatic vital signs, ECGs, urodynamics, and prostate volume measurement). Listings will be ordered by treatment group, subject number, and assessment week or event date. The treatment group presented in listings will be based on the actual treatment assignment in study URO-901-3005 (placebo as 28 Weeks Vibegron 75mg, vibegron 75mg as 52 weeks Vibegron 75mg), unless otherwise noted.

Summary tables will be provided for all subjects who sign informed consent for study URO-901-3006. Unless otherwise specified; all demographic and baseline data and safety data will be presented by treatment group and overall. Unless otherwise specified; all efficacy data will be presented by treatment group. In general, continuous variables will be summarized to indicate the population sample size (N), number of subjects with available data (n), arithmetic mean, SD, median, minimum, Q1, Q3 and maximum values. Categorical variables will be summarized by the population size (N), number of subjects with available data (n), number of subjects in each category, and the percentage of subjects in each category. Unless otherwise noted, the denominator to determine the percentage of subjects in each category will be based on the number of subjects with available data (n) in the analysis set of interest. Select ordinal data may be summarized using both descriptive statistics and counts and percentages of subjects in each category, as appropriate.

The data analyses will be conducted using the SAS[®] System (SAS Institute Inc., Cary, NC) version 9.4 or above. The eClinical Solutions standard operating procedures will be followed for the validation of all SAS programs and outputs.

Formats

Numeric data will be reported at the precision collected on the eCRF. The reported precision from non eCRF sources may be adjusted to a clinically interpretable number of decimal places.

Unscheduled Visits

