Unscheduled visits will be assigned to a study visit using the all-inclusive windows defined in Section 4.2.4. However, data summaries for non-diary data will only report visits that are planned assessment time points for each parameter, according to the Time and Events table. All

visits for bladder diary data will be fully derived as described in section 4.2.4.2. Assessments at unscheduled visits will be included for “any time On-treatment” endpoints and in data listings.

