7.5. Vital Sign Assessments

Vital sign data including blood pressure, pulse rate, respiration rate, body temperature and weight will be collected at all study visits except for the Week 1, Week 16, and 44 telephone visits. Height will be measured at Screening only. Blood pressure will be measured in triplicate at each visit. The average of triplicates will be used for summary. For subjects in URO-901-3005 Study Part 1 at any visits with orthostatic blood pressure measurements: blood pressure (in triplicate) and pulse rate taken pre-dose in sitting position are equivalent to all other pre-dose vital sign values and will be used. Orthostatic and standing blood pressure measurements collected during Part 1 of URO-901-3005 will not be included in any summaries on URO-901-3006.

For all parameters, absolute values and change from baseline will be presented for scheduled visits using descriptive statistics for continuous variables. In addition, the maximum post-baseline change from baseline value and change from baseline to the end of treatment will be summarized for each of the vital signs.

To further investigate changes in SBP/DBP/pulse rate from baseline, the following tables will be prepared:

- Counts and percent of subjects in each group with at least a 5/10/15 CFB at 2 consecutive post-baseline visits and at Week 52 will be produced for all subjects, by pre-existing hypertension category (Yes/No) and by pre-existing hypertension category (Yes/No).
- Maximum post-baseline CFB (including 95% CI of Mean)

The line plot of mean (SE) of change from baseline in blood pressure and pulse rate over time will be prepared. A by-subject listing, sorted by subject identifier, will be presented including all vital sign results (scheduled or unscheduled).

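### The mean maximum vital-sign change in SAP 7.5 sits above zero with no drug effect and is larger over 9 visits than over 3, so its 95% CI and its side-by-side columns mislead

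*SAP*

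**What the plan says.** SAP 7.5 (Vital Sign Assessments) states for every vital sign that "the maximum post-baseline change from baseline value and change from baseline to the end of treatment will be summarized". For systolic pressure, diastolic pressure and pulse it adds a further table, "Maximum post-baseline CFB (including 95% CI of Mean"; the matching entry in the SAP list of output tables is Table 14.3.4.4. Under SAP 4.2.2, "all demographic and baseline data and safety data will be presented by treatment group and overall", so the reader sees a 52-week column, a 28-week column and a pooled column.

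The two groups do not have the same number of readings. SAP 7.5 says vital signs "will be collected at all study visits except for the Week 1, Week 16, and 44 telephone visits". SAP 3.1.2 counts data only from the first vibegron dose, so that "subjects who received placebo in study URO-901-3005 will only contribute safety data up to Week 28". In the extension, "subjects will return to the clinic for visits at Week 28, Week 36, and Week 52" (SAP 1.2.1). SAP 4.2.2 also says "Assessments at unscheduled visits will be included for" any-time on-treatment endpoints. It does not say whether the maximum is one of these.

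Neither SAP 7.5 nor the Table 14.3.4.4 entry equalises the visits or adds a caveat. SAP 7.5 does also plan change from baseline at each scheduled visit, change to end of treatment, and line plots of mean change for blood pressure and pulse. SAP 7 states that no inferential testing is done on safety data.

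**The concern.** The largest of several noisy readings tends to exceed a single baseline reading even if nothing has changed, and the excess grows with the number of readings. Two consequences follow. First, a 95% CI invites comparison with zero, but zero is not the no-effect value of a mean maximum. Second, the column with more visits will show the larger value for reasons of counting alone. Here that is also the column with longer exposure, so the table can look like a rise that grows with time on drug. Hypertension is an adverse event of special interest (protocol 8.4.6) and long-term safety is the primary objective. The extension has no concurrent control column that would expose the artefact.

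**Working it through.** **Planning figure.** The documents give no figure for the mean maximum. The only planning figure is the 100 expected one-year completers (SAP 1.2.4). With 300 subjects split equally and 33% dropout, 300 × 0.5 × (1 − 0.33) = 100.5. This reproduces the 100 and fits about 150 per group, but the allocation ratio is not stated, so 150 is an assumption.

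**Visit counts.**
- 52-week group: SAP Table 4 has 11 post-baseline windows (Weeks 1, 2, 4, 8, 12, 16, 20, 24, 28, 36, 52). Removing the telephone visits at Weeks 1 and 16 leaves 9.
- 28-week group: Visits 12, 13 and 14, which become vibegron Weeks 4, 12 and 28, so 3.

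**Assumptions.** Within-subject visit-to-visit SD of systolic pressure (SD_w) 5 to 10 mmHg, independent normal errors, no true change.

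**Expected mean maximum.** The maximum change is the largest of k post-baseline errors minus the baseline error. The baseline error has expectation zero, so E[max change] = SD_w × m(k), where m(k) is the expected maximum of k standard normals. Numerical integration gives m(3) = 0.846 and m(9) = 1.485. The result is the same whichever reading serves as baseline, so it does not depend on the different wordings of the safety baseline in SAP 3.1.2 and 4.3.4.

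| SD_w (mmHg) | 28-week, 3 visits | 52-week, 9 visits | False difference |
|---|---|---|---|
| 5 | 4.2 | 7.4 | 3.2 |
| 8 | 6.8 | 11.9 | 5.1 |
| 10 | 8.5 | 14.9 | 6.4 |

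The overall column, with equal groups, has expectation (0.846 + 1.485)/2 = 1.17 SD_w, or about 5.8 to 11.7 mmHg.

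**CI width.** The variance of the maximum of k standard normals is 0.559 for k = 3 and 0.357 for k = 9; the baseline error adds 1. The SD of the maximum change is therefore √1.559 = 1.249 SD_w and √1.357 = 1.165 SD_w. The half-width 1.96 × SD/√150 runs from 1.96 × 1.165 × 5/12.25 = 0.93 mmHg to 1.96 × 1.249 × 10/12.25 = 2.0 mmHg.

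**Simulation check** (150 per group, 1000 runs per setting, adjacent-visit error correlation 0 to 0.6, dropout 0 or 33%).
- With SD_w 5 to 10, the false difference was 3.2 to 6.6 mmHg without dropout and 3.7 to 7.9 mmHg with it.
- Each group's CI lay above zero in at least 99.9% of runs, and the two CIs failed to overlap in 95% to 100%.
- Dropout does not close the gap. SAP 3.1.2 requires completion of the 24-week parent period, so a 52-week subject was already scheduled for 6 readings (Weeks 2, 4, 8, 12, 20, 24) before the extension.

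**After matching visits** (Weeks 4, 12 and 28 in both groups, SD_w = 8, no dropout). With independent errors both means are 6.8 mmHg and the difference is zero. With correlation 0.6 the means are 6.0 (52-week) and 4.7 mmHg (28-week), because the matched visits lie more measurements apart in the 52-week group. The upward shift stays in both settings.

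**Consecutive-visit table.** The 52-week group has 9 − 1 = 8 pairs of adjacent visits and the 28-week group 3 − 1 = 2. With no effect, SD_w = 8 and independent errors, about 25% against 11% of subjects reach a rise of at least 10 mmHg at two consecutive visits.

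**The case against.** The strongest reply is that SAP 7.5 already holds the right summaries. Mean change at a fixed visit, change to end of treatment and the mean plots do not carry this bias, and a reader looking for an effect of duration would go to them first. No test or between-group contrast is specified, so the group difference is one that a reader draws from adjacent columns. The hypertension event of special interest rests on consecutive visits or a change in medication (protocol 8.4.6), not on the mean maximum. All of this stands. It makes the point a modest one, but it gives no reason to keep a CI whose reference value is not zero.

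Some stronger readings are tempting, and the documents do not support them.
- A reader might infer that the maximum is positive by construction. That holds for the expected mean when there is no true change. With independent errors about 75% of subjects with 3 visits and 90% with 9 have a positive maximum, and a large enough true fall could make the mean negative.
- A reader might infer that the plan will report a false pressor effect. One descriptive table can look that way; the companion summaries would not bear it out.
- A reader might infer that matching visits cures the problem. It removes the effect of visit count, but about 0.85 SD of upward shift remains, and some difference may persist if errors are serially correlated.
- A reader might want the consecutive-visit categories cut to Weeks 4, 12 and 28 as well. In the 52-week group those weeks are not consecutive, and the cut would discard Weeks 36 and 52 from a long-term safety table.

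**Conclusion.** The concern holds as a cheap improvement to one descriptive safety table. The visit counts of 9 and 3 follow from the SAP. The multipliers 0.85 and 1.49 need only independent normal errors and no true change. The mmHg sizes rest on an SD that the documents do not give, and the CI widths on an assumed 150 per group. The direction does not depend on the SD, and the gap persisted for every correlation and dropout setting tried. Unscheduled readings, if they enter the maximum, would add to the shift. The CI of the mean maximum cannot be read against zero, and the two columns cannot be compared as they stand. Conclusions about average change should come from the fixed-visit and end-of-treatment means.

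**What to change.** In SAP 7.5 and Table 14.3.4.4:
1. Compute the side-by-side and overall maximum over the scheduled visits common to both groups: vibegron Weeks 4, 12 and 28.
2. Show the full-period maximum for the 52-week group in a separate table.
3. Drop the 95% CI of the mean maximum. Place any CI on the mean change at fixed visits and at end of treatment.
4. Add a footnote that the maximum is shifted upward even with no effect, that matching removes the visit-count difference but not this shift, and that some difference may remain under serial correlation.

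Leave the consecutive-visit table over the full period, with a footnote that the 52-week group has 8 visit pairs and the 28-week group 2, so its columns are not directly comparable. When writing that footnote, reconcile the text of SAP 7.5, which says 2 consecutive visits, with the title of Table 14.3.4.2, which says 3.

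The cost is one extra table, a visit restriction in one derivation and two footnotes. The matched table omits some 52-week-group readings, which stay in the separate table.

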7.6. Physical Examination

Brief physical examination data will be collected at Screening, Baseline, Week 12, 24, and 52. A listing of all physical exam results for subjects with at least one abnormal result will be produced.

7.7. Post-Void Residual (PVR) Urine Volume

PVR urine volume data will be summarized at Baseline and every visit. The summary will comprise a continuous summary at each visit, including change from baseline, and a categorical summary of PVR at the following categories: <100 mL, ≥ 100 and < 200 mL, ≥ 200 and < 350 mL, and ≥ 350 mL. All PVR data will be listed.

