2.4.2. Potential Risks

The initial clinical program for vibegron in the treatment of OAB includes subjects of both sexes. It is estimated that the ongoing Phase 3 program in OAB (RVT-901-3003 and RVT-901-3004) will include approximately 15% males, which will contribute to safety data comprising more than 200 men in addition to those enrolled in the URO-901-3005 and URO-901-3006 studies.

Based on aggregate preclinical, clinical pharmacology, and Phase 2 and 3 studies, AEs of special interest (AESIs) predefined for specific evaluations in vibegron clinical studies are as follows:

- Potential major cardiovascular events
- Hypertension
- AEs suggestive of orthostatic hypotension as confirmed by orthostatic vital signs
- AEs suggestive of cystitis or urinary tract infection
- Elevated aspartate transaminase (AST) or alanine transaminase (ALT) laboratory value requiring that the study drug be temporarily withheld or permanently discontinued
- Neoplasm

In addition, the risk for increases in post void residual urine volume and urinary volume will be closely monitored for post-void retention during the study. Study URO-901-3005 enrollment criteria will exclude men with PVR volume ≥ 100 mL at screening and at baseline and those with maximum urinary flow (Q_{max}) less than 5 mL/second. Post-void residual urine volume will be assessed throughout the study, and subjects with a single PVR volume of ≥ 300 mL or an AE of urinary retention will be withdrawn.

Prespecified definitions of urinary retention and other AESIs are provided in the Adverse Event of Special Interest section (Section 8.4.6). More detailed information about the known and expected benefits and risks from the study and reasonably expected AEs of vibegron may be found in the Investigator's Brochure.

[figure not shown]
3. Objectives and Endpoints

Assessments in Study URO-901-3006 are referenced to the initial Baseline (Visit 3) from Study URO-901-3005. Therefore, CFB study endpoints for Study URO-901-3006 are relative to Study URO-901-3005 baseline. At the Week 52 visit, CFB comprises 52 weeks of vibegron exposure for subjects randomized to vibegron in Study URO-901-3005 and 28 weeks of vibegron exposure for subjects randomized to placebo.

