1.1. Study Objectives and Endpoints

Assessments in Study URO-901-3006 are referenced to the initial Baseline (Visit 3) from Study URO-901-3005. Change from baseline (CFB) study endpoints for safety parameters for study URO-901-3006 are relative to the most recent assessment prior to starting vibegron. CFB study endpoints for efficacy in Study URO-901-3006 are relative to Study URO-901-3005 baseline. At the Week 52 visit, CFB comprises 52 weeks of vibegron exposure for subjects randomized to vibegron in Study URO-901-3005 and 28 weeks of vibegron exposure for subjects randomized to placebo.

With respect to study endpoints, “per day” refers to a “Diary Day”, which is defined as the time between when the subject gets up for the day each morning and the time the subject gets up for the day the next morning as recorded in the subject bladder diary (approximately a 24-hour period).

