2. For non-early withdrawal records, if a nominal visit number for a scheduled visit was assigned, then it will be used to summarize the record after checking to make sure that visit numbers match with therapy phases:

- Check that all records entered as a pre-treatment visit for study URO-901-3005 occur on or before the day of the first dose of double-blind treatment (i.e. day ≤1). Any record with day > 1 should be re-slotted to an on-treatment visit using the relative day window below.
- Check that all records slotted to an on-treatment visit for study URO-901-3005 and all records for study URO-901-3006 are on or after the day of the first dose of double-blind treatment. If they are not, the visit should be moved to pre-treatment.

3. Any early withdrawal record (regardless of the visit number assigned), any unscheduled visit record at any time, any repeat visit record, or any record for which the visit number was missing or the visit number was not for a scheduled visit, should be slotted or re-slotted to a visit using the window below.

Table 4: Analysis Visit Window Slotting

Analysis window label	URO-901-3005 Randomized Arm					
	Vibegron			Placebo		
	Nominal visit	Nominal day	Visit Window	Nominal visit	Nominal day	Visit Window
Baseline	Visit 3	1	NA ^a	Visit 3	1	[1,182 ^b]
Week 1	Visit 4	8	[2, 11]	NA	NA	NA
Week 2	Visit 5	15	[12, 22]	NA	NA	NA
Week 4	Visit 6	29	[23, 42]	Visit 12	197	[183 ^c ,224]
Week 8	Visit 7	57	[43, 70]	NA	NA	NA
Week 12	Visit 8	85	[71, 98]	Visit 13	253	[225,308]
Week 16	Visit 9	113	[99, 126]	NA	NA	NA
Week 20	Visit 10	141	[127, 154]	NA	NA	NA
Week 24	Visit 11	169	[155, 182 ^a]	NA	NA	NA
Week 28	Visit 12	197	[183 ^b , 224]	Visit 14	365	> Day 309
Week 36	Visit 13	253	[225, 308]	NA	NA	NA
Week 52	Visit 14	365	> Day 309	NA	NA	NA

a Must have occurred prior to the first dose administered in study URO-901-3005.

b Must have occurred prior to the date of first dose administered in study URO-901-3006.

c Must have occurred on or after the date of first dose administered in study URO-901-3006.

Note: The cut-off days to define the window for slotting through Week 20 are aligned with study URO-901-3005.

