For parameters which were **not** scheduled to be collected at all visits, the all-inclusive visit intervals defined for all visits (i.e., the window defined above) will still be used to slot records. If a value is slotted to a visit unscheduled for a parameter, it will not be summarized (and not be included in the efficacy datasets) but will be included in data listings.

4. If after all records have been slotted or re-slotted, there are multiple valid records within a visit, use the record following the rules below:
 - If there are multiple values for an endpoint in one window, the visit closest to the nominal day will be selected for by-visit displays. If the visits are equidistant from the nominal day, then the earlier visit will be selected. All values will be stored in analysis datasets.

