4.3.4. Baseline and Change from Baseline

In general, the last recorded value on or prior to the date of randomization in the parent study URO-901-3005 will serve as the baseline measurement for efficacy endpoints while the last recorded value prior to first double-blind dose of study treatment will serve as the baseline measurement for safety endpoints. The mean of multiple values will be used as baseline for the following situations:

- If multiple measurements are scheduled on the same baseline day (i.e., blood pressure)
- If multiple measurements are collected on the same baseline day without the time or “repeat” status to differentiate the records

For efficacy endpoints derived from the Bladder Diary, the baseline will be the average value over the diary days in the baseline analysis visit window on study URO-901-3005.

Change from baseline will be calculated as the post-baseline value minus the baseline value. Percentage change from baseline will be calculated as the change from baseline divided by the baseline value, multiplied by 100. If either the baseline or post-baseline value is missing, then change from baseline and percentage change from baseline will be set to missing.

5. Demographics, Other Baseline Characteristics, Procedures And Medication

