11.1.2. Output Figures

Table 10: List of Output Figures

Title		Population	Programming notes
Efficacy Endpoints			
14.2.1.1	Plot of LS Means (SE) of Change from Baseline in Average Daily Number of Micturition Episodes (MMRM)	FAS-Ext	Including all visits
14.2.2.1	Plot of LS Means (SE) of Change from Baseline in Average Daily Number of Urgency Episodes (MMRM)	FAS-Ext	Including all visits

Title		Population	Programming notes
14.2.3.1	Plot of LS Means (SE) of Change from Baseline in Average Number of Nocturia Episodes per Day (MMRM)	FAS-Ext	Including all visits
14.2.4.1	Plot of LS Means (SE) of Change from Baseline in Average Number of Urge Urinary incontinence Episodes per Day (MMRM)	FAS-Ext-I	Including all visits
14.2.5.1	Plot of LS Means (SE) of Change from Baseline in International Prostate Symptom Score (IPSS) Storage Score (MMRM)	FAS-Ext	Including all visits
14.2.6.1	Plot of LS Means (SE) of Change from Baseline in Volume Voided per Micturition (MMRM)	FAS-Ext	Including all visits
Safety Endpoints			
14.3.3.1	Scatter Plot of Maximum ALT Post-Baseline versus Maximum Total Bilirubin Expressed as Multiples of ULN	SAF-Ext	
14.3.3.2	Scatter Plot of Maximum AST Post-Baseline versus Maximum Total Bilirubin Expressed as Multiples of ULN	SAF-Ext	
14.3.3.3	Line Plot of Liver Chemistry Test Results over Time for Subjects with Elevated ALT or AST, and Elevated Total Bilirubin at Any Time	SAF-Ext	Only produce for subjects who potentially met Hy's law
14.3.4.1	Line Plot of Mean (SE) in CFB of Systolic Blood Pressure	SAF-Ext	X-axis starts from baseline visit
14.3.4.2	Line Plot of Mean (SE) in CFB of Diastolic Blood Pressure	SAF-Ext	X-axis starts from baseline visit
14.3.4.3	Line Plot of Mean (SE) in CFB of Pulse Rate	SAF-Ext	X-axis starts from baseline visit
14.3.5.1	Line Plot of Mean (SE) Post-Void Residual Urine Volume	SAF-Ext	X-axis starts from baseline visit, separate lines for treatment groups

Title		Population	Programming notes
14.3.6.1	Line Plot of Mean (SE) IPSS Total Scores	SAF-Ext	X-axis starts from baseline visit, separate lines for treatment groups

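### Part of any PVR rise in the 52-week group is expected from the parent study's 100 mL entry limit, and a difference between groups depends on which of the SAP's two safety baselines governs

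*SAP*

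**What the plan says.** **Selection at entry.** Protocol 2.4.2 states: "Study URO-901-3005 enrollment criteria will exclude men with PVR volume ≥ 100 mL at screening and at baseline". This applied to both parent arms. None of the 11 exclusion criteria in Protocol 5.2 sets a numerical PVR limit for the extension.

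**Display.** SAP 7.7: "PVR urine volume data will be summarized at Baseline and every visit". The summary gives observed values, change from baseline, and four categories, the lowest being below 100 mL. SAP 4.2.2 and Table 1 present safety by group and overall. Figure 14.3.5.1 plots mean PVR with the note "X-axis starts from baseline visit, separate lines for treatment groups".

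**Baseline.** The documents give two definitions and a table that fits neither cleanly.
- SAP 1.1 takes safety changes "relative to the most recent assessment prior to starting vibegron", and SAP 3.1.2 agrees: "Baseline will be established as the last observation prior to the first dose of vibegron".
- SAP 4.3.4 says "the last recorded value prior to first double-blind dose of study treatment will serve as the baseline measurement for safety endpoints". Protocol 9.3.2 also uses the parent baseline for all.
- SAP Table 4 gives ex-placebo men a baseline window of Days 1 to 182, footnoted "Must have occurred prior to the date of first dose administered in study URO-901-3006", but names Visit 3, Day 1 as the nominal visit. With several values in a window, "the visit closest to the nominal day will be selected for by-visit displays".

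**What is left out.** SAP 2.2 and 3.1.2 bring in parent-study safety data only as baseline or after first vibegron. PVR measured on placebo is therefore not summarized, apart from any value serving as baseline.

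**The concern.** Truncating a variable measurement and then using the truncated value as baseline makes later values higher on average, with no treatment effect. Entry deviations aside, the whole 52-week group starts in the lowest PVR category and can only move up.

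Under SAP 1.1 and 3.1.2 the ex-placebo group starts instead from a value taken about 24 weeks after that selection. Table 4 then places both groups on common rows at Weeks 4, 12 and 28 from first vibegron, and the overall column pools them. A change from a truncated baseline sits beside a change from an untruncated one.

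PVR is listed among the endpoints for the primary safety objective, and the protocol's rationale names urinary retention as a safety need particular to these men. The extension has no concurrent control, so change from baseline is the natural reading of its PVR data. The plan offers no reference for how much of a rise selection alone would produce.

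**Working it through.** **1. Figures in the plan.** The documents give no PVR mean, SD, within-man correlation or expected change, so there is no PVR figure to reproduce. The sample-size statement (about 300 men, 33% dropout, 100 completing a year on vibegron) fits a 1:1 split: 300 × 0.5 × (1 − 0.33) = 100.5. The split is an assumption, used below only to set 150 men per group.

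**2. Which value is baseline.**

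| Source | 52-week group | Ex-placebo group |
|---|---|---|
| SAP 1.1, 3.1.2 | parent baseline, truncated | about Week 24, not truncated at 100 mL |
| SAP 4.3.4, Protocol 9.3.2 | parent baseline, truncated | parent baseline, truncated |
| SAP Table 4, read literally | parent baseline, truncated | window to Day 182, but nominal Day 1 |

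On the last row, a Day 1 value is 0 days from nominal and a Day 169 value is 169 − 1 = 168 days away. The closest-to-nominal rule would therefore pick the truncated value.

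**3. Size with no drug effect.** Assumed model, for man i at visit v: PVR = exp[ln(median) + σ(√ρ·uᵢ + √(1−ρ)·eᵢᵥ)], with u and e standard normal, no drug effect and no time trend. Men are kept if screening and baseline are both below 100 mL. Men reaching 300 mL at any of six simulated parent visits are removed, on the assumption that the withdrawal rule in Protocol 2.4.2 also applied in the parent study. Each scenario has 600,000 men. The settings are median 20, 35 or 50 mL; log-SD σ 0.7 or 1.0; correlation ρ from 0.3 to 1.0.

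With baseline per SAP 3.1.2, the 52-week change is Week 28 minus parent baseline and the ex-placebo change is Week 52 minus Week 24. The SE of the difference is √(SD₁²/150 + SD₂²/150).

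| Median, σ, ρ | Baseline mean, 52-wk / ex-placebo (mL) | Change, 52-wk / ex-placebo (mL) | Difference (SE) | Share ≥100 mL, 52-wk | Share ≥100 mL, ex-placebo |
|---|---|---|---|---|---|
| 20, 0.7, 0.9 | 24.2 / 24.3 | 0.1 / 0.0 | 0.1 (1.0) | 0% to 0.3% | 0.3% to 0.3% |
| 20, 0.7, 0.7 | 24.2 / 24.5 | 0.4 / 0.0 | 0.4 (1.8) | 0% to 0.7% | 0.6% to 0.7% |
| 35, 1.0, 0.5 | 32.7 / 40.2 | 8.8 / 1.2 | 7.6 (5.5) | 0% to 7.8% | 7.5% to 7.8% |
| 50, 1.0, 0.3 | 38.6 / 54.5 | 21.3 / 5.4 | 15.9 (8.9) | 0% to 15.5% | 14.5% to 15.5% |
| 35, 1.0, 1.0 | 35.2 / 35.2 | 0.0 / 0.0 | 0.0 (0.0) | 0% to 0% | 0% to 0% |

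For ρ from 0.3 to 0.9, the 52-week rise runs from 0.1 to 21.3 mL, the ex-placebo change from about 0 to 5.4 mL, and the difference from 0.1 to 15.9 mL. At ρ = 1 there is no within-man variation and the artefact vanishes.

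**4. Parent baseline for both groups.** In the middle scenario both changes become 8.8 mL. The difference disappears within simulation error in every scenario, and the rise remains.

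**5. Shape, and what a Week 24 reference removes.** With equal correlation across visits, the rise comes at the first post-baseline measurement. In the middle scenario, with no drug effect, both groups have a Week 24 mean of 40.2 mL, so 40.2 − 32.7 = 7.5 mL of the 8.8 mL is present by Week 24. The Week 28 mean is 32.7 + 8.8 = 41.5 mL, so change from Week 24 is only 41.5 − 40.2 = 1.3 mL. That remainder comes from the assumed removal at 300 mL.

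**The case against.** The strongest reply is that the asymmetry rests on one side of a conflict within the SAP. The section headed as the definition of baseline (4.3.4) caps both groups, and so does the protocol. This stands for the group difference. It does not remove the rise, which then affects both groups.

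The size comes entirely from assumed distributions. That also stands. In the middle scenario the difference of 7.6 mL has an SE of 5.5 mL, so sampling error could hide it, as could a real drug effect or time trend.

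A reader might infer that the table and plot are bound to show a rise and a group gap. The documents support only an expectation, and the gap only under SAP 1.1 and 3.1.2. A reader might also infer an apparent effect that grows with time on vibegron. Selection instead gives a step and then a plateau, which the observed means at each visit would show. Because Figure 14.3.5.1 plots means rather than changes, its gap would lie at the baseline point, with the lines converging afterwards.

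Nor does it follow that a small real effect is impossible to distinguish. Under SAP 3.1.2 the ex-placebo men's before-and-after change is nearly free of this artefact, and the parent study is randomized and placebo-controlled.

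Finally, retention is captured separately as an adverse event of special interest with 200 and 300 mL criteria, and no safety testing is planned. This limits the consequence to interpretation. It does not supply the missing reference in this study's own PVR table.

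**Conclusion.** The point holds as an expected bias in a descriptive safety display. Part of any PVR rise from the parent baseline in the 52-week group is expected from entry selection alone, under either baseline definition. A built-in group difference, in change from baseline or in the share at or above 100 mL, is expected only if SAP 1.1 and 3.1.2 govern.

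Under the assumed distributions the rise runs from negligible to about 20 mL and the difference from about 0 to 16 mL. Neither figure can be narrowed from the documents.

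The conclusion assumes that PVR varies within a man, and that the parent eligibility value at baseline is the same Visit 3 value used as analysis baseline. The parent protocol is not available to confirm the second. The contradiction over the safety baseline needs resolving whatever the size of the artefact.

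**What to change.** 1. Reconcile the safety baseline across SAP 1.1, 3.1.2, 4.3.4 and Table 4, including the nominal visit for ex-placebo men. If the result differs from Protocol 9.3.2, record it in SAP Section 9.
2. In Table 14.3.5.1 add, for the 52-week group, change from Week 24 to Weeks 28, 36 and 52. The 100 mL entry limit does not truncate that reference. It describes the extension period only, since these men have already had 24 weeks of drug.
3. Add the ex-placebo men's PVR from parent baseline to Week 24, labelled as placebo, with the same categories, beside the 52-week group's values for that period. This shows drift without drug.
4. Footnote that the rise from the capped parent baseline is to be read against the placebo-period rise and not, by itself, as a drug effect.

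The cost is SAP wording and a few table rows. The PVR data come from the two studies' existing assessments, and SAP 2.2 places the final analysis after both databases are locked and the parent codes unblinded. The downside is a short placebo block in the extension report, limited to completers who chose to roll over. It is a reference for drift and does not replace the parent study's randomized comparison.
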